4. Design and Procedures: This will be an unblinded, open-label study enrolling newly diagnosed patients with IPF. We plan to consent 50 subjects including screen fails with a goal of obtaining 30 newly diagnosed individuals with IPF prior to initiation of IPF therapies. 20 subjects will be monitored after the initiation of therapy, 10 subjects will be enrolled that do not start antifibrotic therapy. No subject will be excluded from the study on the basis of gender or ethnicity. IPF is an aging disease with highest incidence in subjects >50 years of age, and therefore subjects will be expected to be >50 years of age. Subjects will be obtained from providers in the Duke Pulmonary Clinics. Informed consent will be

Using Xenon MRI to Evaluate the Efficacy of Therapies for Idiopathic Pulmonary Fibrosis

obtained before a subject begins any study intervention. Subjects will undergo an approximately hour long comprehensive MRI protocol, including administration of multiple doses of HP ^{129}Xe . The subjects will have this initial study prior to initiation of IPF therapies. Then the subjects will have repeat studies at 3, 6 and 12 months following the initiation of therapy. Additional studies including pulmonary function studies, serum for biomarkers, 6 minute walk distance (only at screening visit, 3 month and 6 month visit) and a HRCT (only at the screening visit and 6 month visit) will be performed to determine how ^{129}Xe MRI performs relative to standard of care evaluations for IPF. Finally, following the study visits the research team will prospectively follow the patients' clinical course through periodic reviews of the medical record.

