11. Recent exacerbation (within 30 days) defined by the need for antibiotics and/or systemic steroids
12. Medical or psychological conditions which, in the opinion of the investigator, might create undue risk to the subject or interfere with the subject's ability to comply with the protocol requirements

Subject Identification: Subjects will be enrolled in the study by a unique identifier, which will be used for all subsequent analyses. Image acquisition is done by entering the subject's year of birth along with height and weight into the scan set-up page. ^{129}Xe and ^1H MR images will be analyzed with respect to age, gender, heart rate, relevant medical history, and prior image findings. Any such personal health information (PHI) will be obtained

Using Xenon MRI to Evaluate the Efficacy of Therapies for Idiopathic Pulmonary Fibrosis

from the records only by trained clinical research personnel and will then be associated with this unique patient identifier. CT scans will be paid for by grant funds, if not performed for clinical reasons by the provider, and will transferred to PACs.

6. Subject Recruitment and Compensation: Subjects with IPF will be recruited from providers in the Duke pulmonary clinics via flyers, and website postings and from identification at multidisciplinary diagnosis conference. Patients with IPF will be informed about study participation by their physician or a nurse during their clinic visit. If they are interested in participating and appear to meet all inclusion criteria they will be referred to the study coordinator for formal consenting. Recruitment will be open to all demographic groups. Subjects will be compensated \$100.00 after each MRI visit for their travel/parking and time. A total for 4 MRI studies will be performed to complete the study for a total compensation of \$400.00. If a procedure has to be cancelled for technical reasons after a subject has arrived on site, the subject will be compensated as though he/she had completed that visit. The subject will be encouraged, but not required, to return at a later date to complete the procedure. If the subject returns, he/she will be compensated again. Patients may withdraw from the study at any time for any reason.

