4. Breath-hold 3D radial MRI to delineate the thoracic cavity

If any of these scans are deemed by the study team to require repeating, this may be done as needed

HRCT scans will be done in the prone position at both inspiration and expiration using the protocol commonly used in IPF clinical trials.

10. Risk/Benefit Assessment: As this is the first rigorous prospective study of its kind for using MRI to monitor patients with IPF, it is not known if the data generated will be of direct benefit to the patients participating. However, the knowledge gained from these studies is expected to benefit future patients with IPF.

Risks of Hyperpolarized ^{129}Xe Inhalation of hyperpolarized ^{129}Xe may carry some minor risks. Xenon is a general anesthetic when breathed continuously at concentrations greater than 70% for extended periods of time. In the proposed study, xenon will be delivered in a single breath, with alveolar concentrations below 25%. At these concentrations, subjects may experience transient effects including dizziness, slight tingling or numbness of the extremities, nausea, smelling of flowers, or a feeling of well-being and euphoria. These effects will wane within 1-2 minutes of exhaling the xenon and are documented in the consent forms.

Risk of HRCT: Ionizing radiation exposure for the low dose CT is estimated at 2mSievert for each scan. For both inspiratory/and expiratory scans, the total dose is estimated at 4mSievert, roughly the equivalent of 1 year of natural radiation exposure.

A second risk comes from administering HP ^{129}Xe without oxygen. This is necessary to preserve good image quality, because O_2 is paramagnetic and depolarizes the HP ^{129}Xe . Therefore, ^{129}Xe is not mixed with O_2 within the dose delivery bag, but only once it is inhaled. Administration of a single anoxic 1-liter breath has been well tolerated by subjects undergoing both ^3He MRI and ^{129}Xe MRI. After a single breath, the residual oxygen in the subject's lungs is sufficient to maintain blood O_2 saturation during the breath-hold. For each subject, their blood-oxygenation will be monitored throughout the time they are in the MRI scanner. To reduce risk, a baseline resting oxygen saturation of 90% on supplemental oxygen will be required. Furthermore, supplemental oxygen will be provided during the MRI exam as indicated.

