Incidental Findings – Incidental findings will be handled according to the policies of the Duke IRB. That is, anatomic ^1H MR images will not be routinely reviewed by a radiologist. However, if the technologist or study personnel note suspicious findings in the anatomic (^1H) images at the time of MRI, images from those subjects will be reviewed by a radiologist within 10 business days for incidental findings (tumors, hernias, aneurisms, etc). Such incidental findings will be communicated to the subject's physician. Copies of images will be made available to the subject's physician upon their request. If subjects undergo low-

Using Xenon MRI to Evaluate the Efficacy of Therapies for Idiopathic Pulmonary Fibrosis

dose CT as part of this protocol, those scans will be reviewed for incidental findings by a radiologist on the study team.

11. Costs to the Subject and Compensation: There are no additional costs to the subject for the MRI examination and possible CT scan. Subjects will be compensated \$100.00 for travel/parking and time for each study visit. This does not include the initial screening phone call and the phone call to document initiation of IPF therapy.

12. Data Analysis & Statistical Considerations: All images will be reviewed by the study team. Given that this is an early phase study with no clinical experience this will be a research interpretation and not a clinical read. Images and spectra will be analyzed by a variety of quantitative metrics using established methods. Imaging metrics include the ventilation defect percentage (VDP), percentage of lung with high barrier uptake (Barrier_{high}), and percentage of lung with defects in red blood cell transfer (RBC_{low}). Spectroscopic markers will include the ratio of ¹²⁹Xe transfer to RBCs vs barrier (RBC:barrier) as well as RBC oscillation and frequency oscillation amplitudes. CT scans will be evaluated by a chest radiologist using established criteria to produce a mean fibrosis score based on the extent of reticulation and honeycombing and will range from 0-100%.

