Discontinuation - Participation in this study is voluntary and subjects are free to withdraw at any time and for any reason. Furthermore, the individual subject will be withdrawn from the trial should they develop any worsening of health or new medical illness that is deemed to be a result of this study. Parameters to be evaluated include but are not limited to: shortness of breath, heart rate or decreased blood oxygenation related to xenon administration. If a subject experiences a decrease in oxygenation that is greater than or equal to 5% that persists for more than 5 minutes post xenon administration, they will be withdrawn from the trial. Similarly, if patients experience a change in heart rate of more than

Using Xenon MRI to Evaluate the Efficacy of Therapies for Idiopathic Pulmonary Fibrosis

20% or more than one occasion after xenon administration they will be withdrawn. Other reasons for discontinuation include subject becomes uncomfortable in the magnet, subject becomes unresponsive or is unable to protect their airway, subject requests study discontinuation, or other concerns. If any subject experiences a serious adverse drug experience (as defined in 21 CFR Part 312.32(a)), the trial will be discontinued immediately.

14. Privacy, Data Storage & Confidentiality: All consent and case report forms will be stored in a locked filing cabinet in the office of the study coordinator or principal investigator. Any other digital data (images, image analysis) will be associated only with the subject identification number and the date and time of the MRI. Image data will be retrieved and analyzed only by study personnel. The data is stored in a password protected, controlled access account with authentication and mandatory password change features. After all manuscripts have been published the key to the code will be destroyed.

Schedule of Events

Protocol Activities	Screening Phone Call (V0) ¹	Study Visit (V1)	Study Visit (V2)	Study Visit (V3)	Study Visit (V4)	Study Visit (V5)	Prospective Clinical F/U (V6)
Patient phone call	X		X				
Informed Consent ¹		X					
Medical History ²		X		(X)	(X)	(X)	
MRI Screening Form		X		(X)	(X)	(X)	
Pulmonary Function Testing ³		X		X	X	X	
6 minute walk distance ⁴		X		X	X		
Pregnancy Test ⁵		(X)		(X)	(X)	(X)	
HRCT ⁶		(X)			(X)		
MRI Session ⁷		X		X	X	X	
Subject monitoring ⁸		X		X	X	X	
Vital signs		X		X	X	X	
Adverse events followup ⁹		X		X	X	X	
Prospective/Retrospective clinical monitoring in chart ¹⁰							X

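### The plan specifies no masking for the visual CT fibrosis score in an unblinded study, and leaves unclear whether MR images are read with knowledge of history and prior findings

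*Combined protocol and SAP*

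**What the plan says.** Section 4 (Design and Procedures) sets the frame: "This will be an unblinded, open-label study enrolling newly diagnosed patients with IPF". CT is done twice: "a HRCT (only at the screening visit and 6 month visit".

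Section 12 (Data Analysis & Statistical Considerations) states that "All images will be reviewed by the study team". On the xenon measurements: "Images and spectra will be analyzed by a variety of quantitative metrics using established methods". On CT: "CT scans will be evaluated by a chest radiologist using established criteria to produce a mean fibrosis score". That score rests on the extent of reticulation and honeycombing and runs from 0 to 100%.

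Section 5, under Subject Identification, states that "MR images will be analyzed with respect to age, gender, heart rate, relevant medical history, and prior image findings".

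Two further sentences bear on the point. Section 14 (Privacy, Data Storage & Confidentiality) has digital image data "associated only with the subject identification number and the date and time of the MRI". Section 9 (Study Interventions) gives the team discretion over repeats: "If any of these scans are deemed by the study team to require repeating, this may be done as needed". It gives no criteria for this.

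No section mentions masking of a reader, the order in which scans are read, or a second or independent read.

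**The concern.** The CT fibrosis score is a judgement made by eye. A reader who knows which scan is the later one, which drug was taken or what the MRI showed may move the score toward what is expected. The direction cannot be predicted: expecting progression pushes the 6-month score up, and expecting a treatment response pushes it down.

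Two outputs are at stake. Section 12 plans Pearson correlations between the xenon metrics, the CT scores and the clinical tests. A CT score influenced by the MRI result would make the two methods appear to agree better than they do. Section 12 also tests change from baseline with the Wilcoxon signed-rank test at two-sided 0.05, without adjustment for multiple testing. If CT is one of the metrics so tested, a systematic difference in reading between the two visits would look like a real change.

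**Working it through.** **1. The passages side by side**

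| Question | CT fibrosis score | Xenon metrics |
|---|---|---|
| How is the value obtained? | Visual score by a chest radiologist (Section 12) | Quantitative metrics by established methods (Section 12) |
| Is masking to visit, drug or other results stated? | No statement either way | No statement; Section 5 mentions history and prior image findings |
| Is visit order visible? | Not stated for CT | Yes: date and time of the MRI stay with the data (Section 14) |
| Are there discretionary steps? | The scoring itself | Repeat scans at the team's discretion (Section 9) |

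The subject code in Sections 5 and 14 hides identity. It does not hide the sequence of scans.

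**2. The plan's own figures**

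The plan gives no figure for reader bias and no SD for CT change. Its sample sizes, 5 and 19, concern RBC:barrier. They reproduce as n = ((z₀.₉₇₅ + z₀.₉₀) × SD / δ)² with SD 6.6:

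- δ = 10: (3.242 × 6.6 / 10)² = 4.58, rounded up to 5.
- δ = 5: (3.242 × 6.6 / 5)² = 18.31, rounded up to 19.

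Neither depends on how CT is read, so neither changes here.

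**3. Illustration of what a reading shift would do**

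Inputs from the documents: 20 patients followed on therapy, or 30 with the 10 not starting therapy (Section 4); Wilcoxon signed-rank test, two-sided 0.05 (Section 12).

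Assumed, not in the documents: the true change is zero, changes are normal with SD 1, and reading adds a constant shift b to every follow-up score, in SD units of change.

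Test statistic: z = (W⁺ − n(n+1)/4) / √(n(n+1)(2n+1)/24), where W⁺ is the sum of the ranks of the positive changes. For n = 20 the mean is 105 and the SD is √717.5 = 26.8.

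As a cross-check, a one-sample t-test has an exact rejection rate from the noncentral t with n − 1 degrees of freedom and noncentrality b√n. For n = 20 and b = 0.3 the noncentrality is 0.3 × 4.472 = 1.34.

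| Assumed shift b | n = 20, Wilcoxon | n = 20, t-test | n = 30, Wilcoxon |
|---|---|---|---|
| 0 | 4-5% | 5% | 5% |
| 0.1 | 6-7% | 7% | 8% |
| 0.2 | 13% | 14% | 18-19% |
| 0.3 | 23-24% | 25% | 34-35% |
| 0.5 | 54-55% | 56% | 73-74% |

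The Wilcoxon ranges span two simulations, of 4,000 and 200,000 trials per setting. The choice of test makes little difference.

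**4. The correlation**

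A constant shift at one visit leaves the Pearson correlation at that visit unchanged. The correlation is biased if the CT score moves with what the reader knows of the MRI result. The documents do not say whether the CT reader sees that result, so this part is not quantified.

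**The case against.** The strongest reply is that silence is not a plan for unmasked reading. A reader might infer that CT is read with knowledge of visit and drug, because the study is called unblinded. Section 4 uses that word of the study; Section 12 names a radiologist and established criteria and does not address masking. This stands: what can be said is that masking is not specified.

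A reader might also infer from Section 5 that MR images are interpreted with the patient's history and earlier scans in view. The sentence sits under Subject Identification, next to text on how health information is obtained and coded, and Section 12 plans models with clinical and demographic covariates. Covariate use is a fair reading, and comparing later scans with baseline is the purpose of Aim 2. It is not the only reading: prior image findings are not among the covariates that Section 12 names, and the study team reviews all images. The sentence needs clarifying.

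Third, RBC:barrier is a spectroscopic ratio and the documents describe no reader score for it. It would be wrong to extend the argument at equal strength to the xenon metrics. Section 14 speaks of the MRI date, lists no drug, and says nothing of CT labels.

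Fourth, CT is a comparator. Section 3 calls it poorly suited to monitoring response, and CT change is tested only if the plan's reference to each metric includes it. The correlation with CT is planned explicitly.

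Finally, any constant shift inflates a one-sample test, so the table is no evidence that this trial has one. That is correct. It shows only how much a modest shift would matter.

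**Conclusion.** The point holds for the CT score as a missing safeguard: a visual score in an unblinded study, with no statement on masking or reading order. For MR images it holds as an ambiguity in Section 5, with smaller exposure because the metrics are quantitative. The documents do not support the stronger conclusion that images are in fact read unmasked, or that the trial's results are biased.

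The size is unknown. Under the assumptions shown, with 20 patients, a shift of 0.1 SD hardly matters (about 6-7%), while 0.2 to 0.3 SD raises the false-positive rate for CT change to about 13% to 23-24%. These rates should not be applied to RBC:barrier. The case for acting rests on low cost and on protecting the CT-xenon correlation and any CT change score. Open-label treatment is no obstacle to masked reading.

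**What to change.** - **Section 12:** state that the same chest radiologist scores the screening and 6-month CT scans from coded files in random order, masked to date, visit, drug and MRI results. State whether CT change from baseline is among the metrics tested.
- **Section 5:** state that any operator-dependent MR processing is done on coded files, and that medical history and prior image findings enter only as covariates after the metrics are locked.

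The cost is a small amount of file coding and shuffling. CT scoring waits until both scans of a patient are available. No extra reader, scan or patient is needed. The futility analysis after the first 10 patients uses xenon test-retest data, so later CT scoring does not delay it. The review of CT scans for incidental findings in Section 10 is a separate task and keeps its present timing. If scans have already been scored, a masked re-read of the stored images serves the same purpose.

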Using Xenon MRI to Evaluate the Efficacy of Therapies for Idiopathic Pulmonary Fibrosis

median survival time from diagnosis is less than 3 years, and the disease affects an estimated 134,000 Americans, though this prevalence is likely an underrepresentation of the true disease burden. IPF is characterized by gas exchange impairment from thickening of the pulmonary blood-gas barrier. Although high-resolution CT is integral to the initial diagnosis of IPF, it has not proven useful as a means to monitor disease progression or therapy response. As noted by the American Thoracic Society, “*...the diagnosis and management of patients with IPF continues to pose a significant challenge.*” Despite the two recently approved therapies (Nintedanib and Pirfenidone), no IPF therapies have yet been developed that meaningfully reverse this progressive lung fibrosis. Furthermore, genetic and clinical studies clearly demonstrate significant disease heterogeneity. This suggests that IPF patients will require personalization of their therapies. This requires sensitive and accurate measures to assess disease progression and response to treatment. Presently the field is hampered by poor techniques for assessing lung function and development of fibrosis. Therefore, there is a pressing need for improved methods to monitor disease progression and detect response to therapy. It is becoming increasingly clear that the primary roadblock facing the treatment of IPF is not necessarily a lack of viable therapies, but rather a lack of adequate means to test them.

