Although sensitivity to therapy response is expected to be highest for the imaging metrics, the study has been conservatively powered on the basis of the spectroscopic RBC:barrier ratio, which thus far, is most well-documented of the ¹²⁹Xe metrics in the literature. Early studies, which did not control carefully for lung inflation reported a variability of 6.6% in this metric. Moreover, a recent study of natural progression in a group of IPF patients (n=18, on a mix of treatments or untreated) revealed a decline in RBC:barrier of 20% in this metric over the course of 6 months. We assume that we will observe a smaller decline in RBC:barrier in our cohort, which will all receive treatment, and estimate that only a 10% decline will be observed at 12 months. Given this estimate of variability and effect size, and requiring 90% power, would be achieved with a sample of only 5 patients. Based on established patterns in our clinics, we expect roughly half the patients to receive pirfenidone with the other half receiving nintedanib. Assuming that one of the drugs reduces RBC:barrier decline to only 5% over 12 months, whereas the other yields a decline of 10%, would require a sample of 19 patients, which is just achievable with the sample of 20 patients expected to be enrolled.

Baseline Repeatability and Prespecified Futility Analysis – As this is a new clinical study with unknown efficacy in detection a preliminary analysis of the data will be performed. Following completion of the first 10 patients in the study the study team will perform an analysis for futility based on test – retest variability. Baseline repeatability of each of the ¹²⁹Xe metrics will be assessed using Bland- Altman plots, and a pairwise, two-tailed *t*-test will be used to check for significant differences. For each derived parameter, the coefficient of variation will be calculated. Our threshold to stop the study is if the RBC:Barrier ratio is outside of 95% CI on test-retest of $\pm 20\%$ of the dynamic range. We estimate the 95% confidence interval to be better than $\pm 10\%$ with this sample size.

Correlation between ¹²⁹Xe metrics, CT scores, and clinical tests will be evaluated using the Pearson correlation coefficient.

To measure changes from baseline, we will calculate the mean, standard deviation, median and range of each metric, and at each time point, the 95% confidence interval for means and averaged changes relative to baseline will be provided. Changes compared to

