Using Xenon MRI to Evaluate the Efficacy of Therapies for Idiopathic Pulmonary Fibrosis

baseline will be tested using the Wilcoxon Singed-Rank test. In all analyses, $P < 0.05$ (two-sided) will be considered the criterion for statistical significance. There will be no adjustment for multiple testing, because of the small number of hypothesis tests considered. The trajectory changes of these endpoints over time will be evaluated using linear models for repeated measures. Point estimates and confidence intervals for relevant parameters will be provided for descriptive purposes.

Baseline images will be analyzed for functional or structural indicators that may predict therapeutic response using mixed linear models. We will conduct this modeling, while considering differences in treatment group, clinical/demographic covariates (fixed effects), and subject (random effect). Diagnostic plots will be obtained to assess possible violations in model assumptions. All statistical analyses and graphics will be generated in R, or similar statistical package.

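### The sample sizes of 5 and 19 for 90% power use an undefined 6.6% variability as the SD of 12-month change, and 19 is a one-sample size applied to a two-drug comparison

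*Combined protocol and SAP*

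**What the plan says.** Section 12 (Data Analysis & Statistical Considerations) bases power on the spectroscopic RBC:barrier ratio. Its variability input is this: "Early studies, which did not control carefully for lung inflation reported a variability of 6.6% in this metric". For the effect, it cites a natural-progression study of 18 patients with a 20% decline over 6 months, assumes a smaller decline under treatment, and says the authors "estimate that only a 10% decline will be observed at 12 months". It concludes: "Given this estimate of variability and effect size, and requiring 90% power, would be achieved with a sample of only 5 patients".

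It then supposes a 5% decline on one drug and 10% on the other, with about half the patients on each, and says this "would require a sample of 19 patients, which is just achievable with the sample of 20 patients expected to be enrolled".

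The same section sets the significance criterion ("In all analyses, $P < 0.05$ (two-sided) will be considered the criterion for statistical significance") and names the Wilcoxon signed-rank test for changes from baseline. It gives no SD of 12-month change, no formula or test for the power statements, and no allowance for losses, although section 4 (Design and Procedures) foresees patients lost before completing the in-person visits.

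**The concern.** The power of a test on change from baseline depends on how much the change varies between patients. That variance has two parts: the measurement error of the two scans, and the spread of true decline from patient to patient. The plan's only input is a variability of the metric, mentioned together with poor control of lung inflation. Lung inflation affects a scan, not the pace of disease, so the natural reading is measurement variability. If so, the second part is missing, although section 3 (Background and Significance) says that "genetic and clinical studies clearly demonstrate significant disease heterogeneity".

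The drug comparison has a further difficulty. It contrasts two groups, yet its size is set against the total of 20 treated patients as if one group were enough.

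These two sizes are the only quantitative support for the treated sample. If they are too low, readers are given a wrong picture of the margin for the 10% decline and of whether the drugs can be compared at all.

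**Working it through.** **Inputs from section 12.** Two-sided alpha 0.05 (z = 1.960); power 90% (z = 1.282); variability 6.6%; decline 10%; drug difference 10 − 5 = 5 points. Section 4 gives 20 treated patients.

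**Reproducing the plan.** The one-sample normal formula is n = (1.960 + 1.282)² × SD² / delta² = 10.507 × SD² / delta².

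- SD 6.6, delta 10: 10.507 × 43.56 / 100 = 4.58, so 5.
- SD 6.6, delta 5: 10.507 × 43.56 / 25 = 18.31, so 19.

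Both match exactly. So 6.6 was used unchanged as the SD of each patient's 12-month change, and 19 is a one-sample size.

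**What 6.6% could be.** Let m be the measurement SD of a difference between two scans and tau the between-patient SD of true decline. Then SD of change = √(m² + tau²).

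- Reading A: 6.6% is the SD of a repeat-scan difference, so m = 6.6. The plan's figures then require tau = 0.
- Reading B: 6.6% is the error of one scan, so m = 6.6 × √2 = 9.33. The SD used is then below scan noise alone.

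**Size needed for the 10% decline.** Tau is not in the documents; the values below are assumptions. Needed n and power at n = 5 use the plan's normal formula, with power = Φ(10√5/SD − 1.960). The last column is a two-sided paired t test with 20 patients.

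| Reading | tau | SD of change | n needed | Power at n = 5 | Power at n = 20 |
|---|---|---|---|---|---|
| A | 0 | 6.60 | 5 | 92% | >99% |
| A | 5 | 8.28 | 8 | 77% | >99% |
| A | 10 | 11.98 | 16 | 46% | 94% |
| A | 15 | 16.39 | 29 | 28% | 74% |
| B | 0 | 9.33 | 10 | 67% | >99% |
| B | 5 | 10.59 | 12 | 56% | 98% |
| B | 10 | 13.68 | 20 | 37% | 87% |
| B | 15 | 17.67 | 33 | 24% | 67% |

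With 20 patients, paired t-test power for a 10% decline stays at 90% up to an SD of change of 13.08.

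The normal formula is itself optimistic at such sizes. With SD 6.6 kept, a paired t test needs 7 patients, and 5 give 72% power. With 5 patients the smallest two-sided exact signed-rank p is 2/2⁵ = 0.0625, so the planned test could not reach significance.

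**Drug comparison as two groups.** n per arm = 2 × 10.507 × SD² / delta². With SD 6.6 and delta 5: 2 × 18.31 = 36.6, so 37 per arm (38 by the t test), or 74 to 76 in total against the stated 19. With 10 per arm, t-test power is 36% at SD 6.6, 21% at SD 9.33 and 12% at SD 13.68.

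**The case against.** The strongest reply is that 6.6% is undefined. If it were already an SD of longitudinal change, the criticism of the SD would fall. That possibility cannot be excluded, but nothing in section 12 says so and the lung-inflation remark points the other way. Even then, 19 would remain a one-sample size.

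The reply is also right that the evidence on spread is thin. The heterogeneity sentence in section 3 is general and gives no spread of RBC:barrier change. The plan's own 5%/10% scenario, split evenly, implies a between-patient SD of only 2.5 points; on reading A this raises 4.58 to 10.507 × (43.56 + 6.25)/100 = 5.23, so 6 patients with the mean decline held at 10%. The larger values of tau have no anchor in the documents.

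Four stronger readings are tempting, and the documents do not support them:

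- A reader might infer that the plan assumes every patient declines by the same percentage. That follows only on reading A; on reading B the SD is too small for another reason.
- A reader might infer that the study cannot detect a 10% decline. Nobody plans to stop at 5 patients, and 20 are adequate over much of the range shown.
- A reader might infer that correcting the SD would repair the 19. It would not, because the two-group structure is the larger error.
- A reader might call the word *conservatively* false. In its sentence it describes the choice of the spectroscopic ratio over imaging metrics expected to be more sensitive, and the assumed decline is also smaller than the one cited.

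**Conclusion.** The point stands in limited form. The 90% power claimed at 5 and 19 patients rests on treating an undefined variability of the metric as the SD of 12-month change, and the plan offers no support for that. On reading A any spread in true decline breaks the claim; on reading B scan noise alone does. How far 5 is too low cannot be settled from the documents, because no SD of change is given.

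For the 10% decline the consequence is mainly an unsupported statement, since 20 treated patients leave room up to an SD of change of about 13.1 before losses. For the drug comparison the consequence is substantive: at about 10 per arm it is underpowered at every SD considered, including the plan's own 6.6.

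**What to change.** Change the wording of section 12 only:

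- Define the 6.6%: a coefficient of variation, a single-scan SD, or the SD of a repeat-scan difference.
- Base power on an SD of within-patient 12-month change. Use the observed SD of change from the 18-patient serial study if it can be obtained, noting that it covers 6 months and already contains scan noise, so no further noise term should be added. Otherwise state a range.
- Delete the figures of 5 and 19.
- State what 20 treated patients deliver for a 10% decline: by paired t test, 90% power if the SD of change is at most about 13.1, 87% at 13.7 and 67% at 17.7. Confirm these for the planned Wilcoxon signed-rank test and allow for losses to follow-up.
- For the drug comparison, state the two-group power at about 10 per arm, or call the comparison exploratory.

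The word *conservatively* may stay as a description of the choice of metric. The cost is a less favourable power statement; enrolment does not change.
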